9. OVERALL STATISTICAL CONSIDERATIONS

9.1. GENERAL CONVENTIONS

Summary statistics will be presented for categorical data as number and percentage [n (%)] where the percentage is displayed to one decimal point (e.g., 98.1).

Descriptive statistics will be presented for continuous data with applicable decimal precision as follows in relation to the source data (indicated as N), with a maximum of three decimals to be displayed:

- Number (n).
- Mean, (N+1).
- SD, (N+2).
- Median, (N+1).
- Minimum, (N+0).
- Maximum, (N+0).

Study day is calculated relative to the first dose of study drug infusion and will thus in most cases coincide with the visit naming (e.g., Day 1 will be on study day = 1, Day 15 will be on study day = 15 etc.)

- If the current assessment/collection/result (ACR) date is on or after first dose of study drug infusion:

$$\text{Study Day} = (\text{Current ACR Date} - \text{First dose of Study Drug infusion Date}) + 1$$

- If the current ACR date is before first dose of study drug infusion:

$$\text{Study Day} = (\text{Current ACR Date} - \text{First dose of Study Drug Infusion Date})$$

Study day will not be calculated if either the current ACR or the first dose of study drug infusion date is incomplete or missing.

All the tables in Part 1, will be displayed by treatment groups (i.e., TB006 140 mg qw, TB006 420 mg qw, TB006 1000 mg qw, and Pooled placebo).

The dispositions, efficacy, PK/PD, biomarker, and immunogenicity analysis for Part 2 will be classified by treatment groups (i.e., TB006 and Placebo) and baseline AD severity stratifications [i.e. mild AD (MMSE 21-24) and moderate-severe AD (MMSE ≤ 20)]. For efficacy tables of Part 2, the subjects enrolled at the same TB006 dose level in Part 1, as well as all placebo patients will be included.

For all baseline, safety and efficacy assessments, the subjects will be tabulated using the actually received treatment. For example, if there is a subject who is planned to receive TB006 but accidentally gets treated with one of the other regimens, the subject will be tabulated under the other regimen actually received.

The tables and listing for both protocol parts will be presented separately. The detailed layout will be presented in mock shell.

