9.3 Populations for Analyses

For the purposes of analysis, the following analysis sets are defined:

Full analysis set (FAS)	All patients who are randomly assigned to study drug
Safety analysis set (SAS)	All patients randomly assigned to study drug and who take at least 1 dose of study drug. Patients will be analyzed according to the study drug they actually received
PK analysis set (PKS)	All patients who received at least 1 dose of TB006 and have at least 1 post-dose blood sample with measurable TB006 concentrations
PD analysis set (PDS)	All patients who received blinded study drug and have at least 1 post-dose evaluable PD assessment

The FAS will be used for the analysis of disposition and protocol deviations. The SAS will be used for all other analyses, except specifically for PK and PD. The FAS and the SAS will be the

Protocol TB006AD2102

Protocol Date and Version: 15 Oct 2021; v 3.0

same if all randomized patients are dosed with study drug. The PKS will be used for all PK analyses and the PDS will be used for all PD and efficacy analyses.

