7.1.4. PHARMACODYNAMIC ANALYSIS SET (PDS)

The Pharmacodynamic Analysis Set (PDS) includes all subjects who received assigned dose of TB006 or placebo and have at least one post-dose evaluable PD assessment. The PDS will be used for all PD and efficacy analyses.

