7.1.5. EFFICACY ANALYSIS SET – PART 2 (EAS2)

The Part 2 – Efficacy Analysis Set (EAS2) includes all subjects who received assigned dose of TB006 in Part 2 and the subjects enrolled at the same TB006 dose level in Part 1, as well as all placebo patients will be included and have at least one post-dose evaluable PD assessment across subject. The EAS2 will be used for all efficacy analysis planned for Part 2 of the study.

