9.5. MMRM METHOD

The primary and secondary efficacy endpoints associated with efficacy assessments listed in Section 9.4.2 will be analyzed using a MMRM model. The model will include treatment group, visit, stratification factor (MMSE \leq 20 and 21-24), and treatment by visit as fixed effects and associated baseline assessment as covariate. The model will use visit as repeated component in the model.

An unstructured (UN) covariance structure will be applied for the MMRM. In the event the UN covariance matrix results in non-convergence of the model, then the Heterogeneous Toeplitz (TOEPH) and auto regressive [i.e. AR(1)] covariance structures will be used, respectively, with separate subject random effect. The Kenward-Roger (KR) approximation will be used to estimate denominator degrees of freedom.

The least square (LS) mean for CFB and associated 95% confidence interval (CI), and standard error will be presented for each treatment group.

The MMRM model will utilize all available data values for respective efficacy assessments.

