11. EFFICACY PARAMETERS

All the efficacy analysis planned for Part 1 will be performed using PDS and efficacy analysis planned for Part 2 will be performed using EAS2. The EAS2 include all PDS subjects of Part 2, placebo subjects of Part 1 and subjects with same dose level in Part 1 pooled together.

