11.1. PRIMARY ANALYSIS

There is no primary efficacy analysis planned for Part 1.

For Part 2, the CFB through Day 104 on the CDRS – Sum of Boxes total score is primary efficacy endpoint, and it will be analyzed using MMRM with treatment group, randomization strata (MMSE \leq 20 and 21-24), visit, and treatment group (treated vs. placebo) by visit interaction as fixed effects and a baseline CDRS - Sum of Boxes score as a covariate. The LS mean difference, the 95% CI of the difference, and the p-value will be presented as well as the descriptive statistics.

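### The SAP groups Part 2 efficacy by treatment received and narrows the efficacy set to patients given their assigned dose; the rules conflict, and neither is declared as a change from Protocol 9.3 (minor)

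*SAP*

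**What the plan says.** **Grouping.** SAP 9.1 applies one rule to baseline, safety and efficacy: "For all baseline, safety and efficacy assessments, the subjects will be tabulated using the actually received treatment". Its example is a patient planned for TB006 who "accidentally gets treated with one of the other regimens, the subject will be tabulated under the other regimen actually received".

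**Entry to the efficacy sets.** The PDS in SAP 7.1.4 "includes all subjects who received assigned dose of TB006 or placebo and have at least one post-dose evaluable PD assessment". The Part 2 efficacy set (EAS2) in SAP 7.1.5 "includes all subjects who received assigned dose of TB006 in Part 2", then adds Part 1 patients at the same dose level and all placebo patients. The addendum changes the type of post-dose assessment required, from PD to efficacy, and keeps the assigned-dose wording. In 7.1.5 that wording attaches to Part 2 TB006 patients only. It reaches Part 2 placebo patients through 7.1.4 and SAP section 11: "The EAS2 include all PDS subjects of Part 2, placebo subjects of Part 1".

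**Model terms.** SAP 9.5: "The model will include treatment group, visit, stratification factor". SAP 11.1 lists "treatment group (treated vs. placebo) by visit interaction as fixed effects". Neither section says whether treatment group means the randomised or the received arm.

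**Protocol 9.3.** The PDS, used for efficacy, is "All patients who received blinded study drug and have at least 1 post-dose evaluable PD assessment". Analysis by drug received is stated only in the definition of the safety set. No grouping rule is given for the PDS.

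**Declared changes and other analyses.** The only item in SAP section 8 is dose proportionality. SAP 7.1.1 uses the full analysis set for disposition and deviations only. SAP 11.3 plans no sensitivity analysis.

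**The concern.** Randomisation protects an efficacy comparison only if patients are kept in the arm to which they were allocated. SAP 9.1 gives that up for efficacy, and the set definitions give it up in a different way. If a dosing error is related to prognosis, moving or dropping the patient biases the treatment difference. For the Sum of Boxes, MMSE and NPI, the visible SAP specifies no as-randomised analysis that would show by how much.

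The rules also cannot both be applied. A patient excluded for not receiving the assigned dose cannot then be tabulated under the dose received. Each patient is to have five infusions (Protocol 6.1, Table 4), and nothing says how many must be as assigned. Someone would have to choose when a case arises. Under Protocol 8.5, unblinding drug concentrations are withheld from blinded personnel until the study is unblinded. My inference is that an error first seen in the PK data could reach the analysis team only after unblinding, when the choice of rule would be open to criticism.

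**Working it through.** **1. The plan's figure.** Inputs from Protocol 9.2 and SAP 6.1.1: 64 per arm, SD 0.5, difference 0.25, two-sided 5% t-test.
- SE = 0.5 × √(2/64) = 0.0884, with 126 df.
- Noncentral t power at 0.25 is 80.1%, which agrees with the stated 80%.

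**2. What happens to a mis-dosed patient.**
- Wrong treatment throughout: moved under SAP 9.1, or excluded under 7.1.4, 7.1.5 and section 11. Neither keeps the patient as randomised.
- Some infusions wrong: 9.1 does not say which treatment counts as received, and the set definitions do not say whether all five infusions must be as assigned. Such a patient might stay in the randomised arm.

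**3. Bias.** The documents give no mis-dosing rate and nothing linking errors to prognosis, so the following are assumptions. Suppose there is no drug effect, k of 64 patients in one arm are mis-dosed, and they differ by d from the rest of that arm. Put f = k/64. If the unaffected patients average r, the full arm averages r + fd, and so does the other arm.
- Excluded: shift = fd.
- Moved: the receiving arm averages r + 2kd/(64 + k), so shift = 2fd/(1 + f).
- Worked for k = 1, d = 0.5: excluded 0.5/64 = 0.0078; moved (2 × 0.5/64)/(1 + 1/64) = 0.0154.

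| k | d | Shift, excluded | Shift, moved | Type I error, excluded / moved |
|---|---|---|---|---|
| any | 0 | 0 | 0 | 5.0% / 5.0% |
| 1 | 0.25 | 0.004 | 0.008 | not tabulated |
| 1 | 0.5 | 0.008 (3% of 0.25) | 0.015 (6%) | 5.1% / 5.3% |
| 2 | 0.5 | 0.016 (6%) | 0.030 (12%) | 5.4% / 6.3% |
| 3 | 0.5 | 0.023 (9%) | 0.045 (18%) | 5.8% / 7.9% |

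The two shifts are alternatives and do not add. One patient is the more realistic case; two and three are stress cases. The direction is unknown, and similar errors in both arms would largely cancel.

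**4. Power cost of analysing as randomised.** Suppose k TB006 patients receive only placebo and lose the whole effect. The expected difference is 0.25 × (1 − k/64).
- k = 1: 0.246, power 78.9%. With errors unrelated to prognosis, exclusion would give 79.8% and moving 80.1%.
- k = 3: 0.238, power 76.3%, against 79.2% and 80.1%.

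**The case against.** **The protocol does not promise as-randomised efficacy.** This stands. A reader might infer that SAP 9.1 contradicts Protocol 9.3. It does not: the protocol is silent on grouping for the PDS, so the as-received rule for efficacy is an undeclared addition. The departure from the protocol's text is the entry condition.

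**The filter may be loose drafting.** The same substitution appears in the PK set (Protocol 9.3 against SAP 7.1.3). In 7.1.5 the phrase may only identify the Part 2 dose, which the plan allows to be adjusted. That is possible, so exclusion is the literal reading and not a settled one. It is also a reason to clarify.

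**The word used in 9.1 may cover tables only.** If so, nothing else in the visible SAP defines the model's treatment term as the randomised arm, and the entry filter remains.

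**The gap may be filled elsewhere.** The Cognitive Drug Research battery has its own SAP, which is not available, and text after SAP 11.3 is redacted. The point is therefore limited to what the visible SAP specifies for the Sum of Boxes, MMSE and NPI.

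**Errors are unlikely and would be seen.** Central IWRS assignment, labelling by randomisation number (Protocol 6.4.1) and second-person confirmation of each dose (Protocol 6.5) make errors unlikely. Displays in SAP 10.1 and 10.7 would show the patient. This keeps the point small, but those displays give no as-randomised estimate.

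**The primary comparison is already pooled.** It combines 58 per arm randomised 1:1 in Part 2 with about 6 per arm from Part 1 groups randomised 6:2. The point concerns only keeping each patient's randomised assignment within that pool.

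**Conclusion.** The point holds as a minor one. SAP 9.1 conflicts, read literally, with 7.1.4, 7.1.5 and the addendum. The changed entry condition is an undeclared departure from Protocol 9.3, and as-received grouping for efficacy is an undeclared addition to it.

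Two stronger readings are tempting. A reader might infer that no mis-dosed patient is ever analysed as randomised. The text supports this only for a patient mis-dosed throughout, because the assigned-dose wording does not require all five infusions. A reader might also take the 7.9% type I error as an expected consequence. It needs three patients, all in one arm, all moved, and all a full planning SD from the rest of that arm; nothing in the documents suggests this.

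In the one-patient case, with an assumed difference of 0.5 points, the bias is 0.008 to 0.015 against 0.25 and type I error is 5.1% to 5.3%. With no mis-dosing, or errors unrelated to prognosis, bias is zero. Confidence is high on the wording and low that it would ever change the result.

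**What to change.** 1. In SAP 9.1, take efficacy out of the as-received rule and keep that rule for safety, exposure and PK. State that the MMRM (9.5, 11.1, 11.2) and the CMH test (11.2.2) use the randomised arm. For Part 1 patients this means the dose group in which they were enrolled and the arm to which they were randomised within it.
2. In SAP 7.1.4, and in 7.1.5 as restated by the addendum, restore the protocol's condition of having received blinded study drug, for both arms and however many infusions were as assigned. Keep each set's post-dose assessment condition. Section 11 inherits the change through the PDS.
3. List any remaining difference from Protocol 9.3 in SAP section 8.

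A supportive as-received efficacy analysis is optional; including it means reporting efficacy twice.

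**Cost.** A few sentences and a randomised-arm variable in the efficacy programs, with no extra patients or data. The planned 128 patients and 80% power are unchanged if nobody is mis-dosed. If one TB006 patient receives placebo throughout, power falls from 80.1% to 78.9%.

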9.2. BASELINE DEFINITION

Baseline is defined as the last available value prior to the subject receiving first dose of study drug infusion (i.e., Day 1). If the potential Baseline ACR is on Day 1 (and time is not recorded), it is assumed that the ACR occurred before the start of first dose of study drug infusion.

CFB is calculated as:

$$\text{CFB} = \text{Observed value} - \text{Baseline Value}$$

Percentage change from Baseline (CFB%) is calculated as:

$$\text{CFB\%} = (\text{CFB} \div \text{Baseline Value}) \times 100$$

9.3. HANDLING OF PK CONCENTRATION VALUES BELOW LOWER LIMIT OF QUANTIFICATION

For PK concentrations, values that are below the lower limit of quantification (BLQ) the following handling measures will be applied:

- For NCA, pre-dose concentrations prior to the first dose of TB006 that are BLQ will be set to zero. Post-dose concentrations that are BLQ and occur before the first quantifiable concentration will also be treated as zero. Post-dose concentrations that are BLQ but occur after the first quantifiable concentration will be treated as missing.
- For summary statistics, BLQ concentrations will be treated as zero.
- In listing presentation these values will be marked/footnoted as being BLQ.

9.4. HANDLING OF MISSING DATA

No formal imputation of missing data is planned for Part 1 of the study. There are however a few handling conventions and assumptions applicable to partial/missing data points which are described in the following subsections.

9.4.1. PARTIAL DATES

Although partial dates will not be 'filled up' in this study, some assumptions will be made in regards partial dates for background calculation/classification purposes as appropriate (for AEs, prior/concomitant medications etc.)

Table 1. Handling of Partial Dates

Parameter	Missing	Additional Conditions	Imputation
Start date	D	M and Y same as M and Y of first dose of study drug	Date of first dose of study drug
		M and/or Y not same as date of first dose of study drug	First day of month
	D and M	Y same as Y of first dose of study drug	Date of first dose of study drug
		Y prior to Y of first dose of study drug but same as Y of screening date	Date of screening date
	D, M and Y	None - date completely missing	Date of first dose of study drug
Stop date	D	M and Y same as M and Y of last dose of study drug	Date of last dose of study drug
		M and/or Y not same as date of last dose of study drug	Use last day of month
	D and M	Y same as Y of last dose of study drug	Date of last dose of study drug
		Y not same as Y of last dose of study drug	Dec 31
	D, M and Y	None - date completely missing	No imputation, but assume ongoing

D = day, M = month, Y = year
Note: In all cases, if an estimated start date is after a complete stop date, use the first day of the stop date month. Similarly, if the estimated stop date is before a complete or imputed start date, use the last day of the start day month.
In all cases, if it cannot be determined if the AE/medication occurred prior to or after the first dose of study drug infusion, the AE should be defined as treatment emergent, and medication will be considered as concomitant medication.

9.4.2. MISSING VALUE IMPUTATION FOR EFFICACY ENDPOINTS – PART 2

Apart from handling conventions and assumptions applicable to partial/missing data points mentioned above, there will be additional imputation for missing efficacy assessments listed under:

- CDRS – Sum of Boxes total score
- MMSE score
- NPI score

For these imputations, the missingness will be considered as missing at random (MAR). There will be no imputation for individual missing values, but missing data will be imputed implicitly using Mixed Model Repeated Measures (MMRM).

The MMRM analysis will be performed for above listed efficacy endpoints as described in Section 9.5.

9.5. MMRM METHOD

The primary and secondary efficacy endpoints associated with efficacy assessments listed in Section 9.4.2 will be analyzed using a MMRM model. The model will include treatment group, visit, stratification factor (MMSE \leq 20 and 21-24), and treatment by visit as fixed effects and associated baseline assessment as covariate. The model will use visit as repeated component in the model.

An unstructured (UN) covariance structure will be applied for the MMRM. In the event the UN covariance matrix results in non-convergence of the model, then the Heterogeneous Toeplitz (TOEPH) and auto regressive [i.e. AR(1)] covariance structures will be used, respectively, with separate subject random effect. The Kenward-Roger (KR) approximation will be used to estimate denominator degrees of freedom.

The least square (LS) mean for CFB and associated 95% confidence interval (CI), and standard error will be presented for each treatment group.

The MMRM model will utilize all available data values for respective efficacy assessments.

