9.2 Sample Size Determination

In Part 1, patients will be recruited sequentially in separate increasing dose groups, with each group randomizing 6 patients to a specific dose of TB006 and 2 randomized to placebo. If all 3 planned dose levels are investigated, the study will recruit approximately 24 patients in total (18 receiving TB006 treatment at the different dose levels, and 6 receiving placebo).

In Part 2, patients will be randomized to TB006 or placebo in a 1:1 ratio so that approximately 58 patients will be randomized to each group. Randomization in Part 2 will be stratified according to baseline patient severity, with mild AD patients (MMSE 21-24) and moderate-severe AD patients (MMSE \leq 20) in each strata. Patients enrolled at the same TB006 dose level in Part 1, as well as all placebo patients, will be included in the efficacy analyses in Part 2. Thus, the number of patients in each group for the primary efficacy analysis will be approximately 64.

Assuming that the standard deviation of change from baseline Clinical Dementia Rating Scale – Sum of Boxes at Day 104 is 0.5, a total of 128 patients will provide 80% power to detect a mean change from baseline difference of 0.25 at Day 104 using a 2-sided, 2 sample t-test at the 5% level of significance.

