6.1.1. JUSTIFICATION OF SAMPLE SIZE

In Part 1, patients will be recruited sequentially in separate increasing dose groups, with each group randomizing 6 patients to a specific dose of TB006 and 2 randomized to placebo. If all 3 planned dose levels are investigated, the study will recruit approximately 24 patients in total (18 receiving TB006 treatment at the different dose levels, and 6 receiving placebo).

In Part 2, patients will be randomized to TB006 or placebo in a 1:1 ratio so that approximately 58 patients will be randomized to each group. Randomization in Part 2 will be stratified according to baseline patient severity, with mild AD patients (MMSE 21-24) and moderate-severe AD patients (MMSE ≤ 20) in each stratum. Patients enrolled at the same TB006 dose level in Part 1, as well as all placebo patients, will be included in the efficacy analyses in Part 2. Thus, the number of patients in each group for the primary efficacy analysis will be approximately 64.

Assuming that the standard deviation (SD) of change from baseline (CFB) Clinical Dementia Rating Scale (CDRS) - Sum of Boxes at Day 104 is 0.5, a total of 128 patients will provide 80% power to detect a mean CFB difference of 0.25 at Day 104 using a 2-sided, 2 sample t-test at the 5% level of significance.

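### The MMRM has no baseline-by-visit term, which may cost some precision at Day 104, and its last-resort AR(1) covariance assumes one variance for every visit

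*SAP*

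**What the plan says.** SAP 9.5 gives the MMRM for the primary and secondary efficacy scores. The fixed effects are treatment, visit, the MMSE stratum, and "treatment by visit as fixed effects and associated baseline assessment as covariate". SAP 11.1 and protocol 9.4.5 state the same primary model, with baseline CDR Sum of Boxes as a single covariate. Protocol Table 2 schedules four post-baseline CDR assessments: Days 15, 36, 64 and 104.

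The covariance is unstructured. Only on non-convergence does SAP 9.5 move to heterogeneous Toeplitz and then AR(1), which "will be used, respectively, with separate subject random effect". Degrees of freedom are Kenward-Roger, and no robust standard error is named. SAP 11.3 plans no sensitivity analysis.

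**The concern.** A baseline main effect forces the same slope on change at two weeks and change at fifteen weeks. In patients ranging from mild to severe disease, baseline severity may well predict late change differently from early change. The fitted common slope is then a weighted compromise. If early visits are less variable, they dominate it and Day 104, the visit on which the study is powered, is under-adjusted.

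The fallback raises a different issue. AR(1) plus a subject effect has one variance for all visits and treats gaps of 21, 28 and 40 days as equal. If the SD of change grows towards Day 104, the pooled variance is too small there and the primary test becomes anti-conservative. With no sensitivity analysis planned, no other analysis would reveal either problem.

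**Working it through.** **Inputs from the documents.** The test is made "using a 2-sided, 2 sample t-test at the 5% level of significance"; "a total of 128 patients will provide 80% power"; the target is a "mean change from baseline difference of 0.25 at Day 104"; the SD is stated as "Sum of Boxes at Day 104 is 0.5"; "the number of patients in each group for the primary efficacy analysis will be approximately 64"; and "patients will be randomized to TB006 or placebo in a 1:1 ratio".

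**Reproducing the plan.** Unadjusted SE = 0.5 × √(2/64) = 0.0884. The exact two-sample t-test gives 80.1% power, so the stated 128 is confirmed. The normal approximation, Φ(0.25/SE − 1.96), gives 80.7% and is used below for comparisons.

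**Assumed inputs.** The documents give no baseline SD, no SD of change before Day 104, no visit correlations and no baseline slopes. I assume that baseline explains 5%, 10% or 20% (R²) of Day 104 change variance, that the slope grows in proportion to time, that between-visit residual correlation is 0.5 or 0.7, and that the SD of change is either flat at 0.5 or rises linearly in time from 0.25, 0.30 or 0.35 at Day 15 to 0.5.

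**Common slope.** Let b be the vector of visit-specific slopes per SD of baseline, with b₁₀₄ = 0.5√R², and W the residual covariance when one slope is fitted. Generalised least squares gives g = (1′W⁻¹b)/(1′W⁻¹1). Then

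- by-visit SE = √[(2/64) × 0.25(1 − R²)]
- common-slope SE = √[(2/64) × {0.25(1 − R²) + (b₁₀₄ − g)²}]
- share of adjustment kept = 1 − [(b₁₀₄ − g)/b₁₀₄]²

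Example: R² = 10%, Day 15 SD 0.30, correlation 0.5. Here b₁₀₄² = 0.025 and g/b₁₀₄ = 0.249, so (b₁₀₄ − g)² = 0.025 × 0.751² = 0.0141. By-visit SE = √(0.225/32) = 0.0839, power 84.6%. Common-slope SE = √(0.2391/32) = 0.0864, power 82.4%.

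| R² | Power, by-visit slope | Common slope, flat SD | Common slope, rising SD |
|---|---|---|---|
| 5% | 82.7% | 82.3% | 80.7-81.8% |
| 10% | 84.6% | 83.9-84.0% | 80.7-82.9% |
| 20% | 88.5% | 87.4-87.8% | 80.9-85.3% |

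The loss is 0.4-1.1 points with flat SD and 0.9-7.6 points with rising SD. The share kept is about 80-90% with flat SD. With rising SD it runs from about zero to 59%, and is below half in 15 of 18 combinations. With a constant slope g = b₁₀₄, so nothing is lost.

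Other shapes widen the range. At a baseline correlation of 0.3 (R² = 9%), letting the slope grow as √time or appear late, with several SD patterns, the cost against the by-visit slope ran from 0 to 6 points (84.3% down to 78.2%). The harshest case tried (correlation 0.5, late-appearing slope, SD proportional to time) fell from 90.4% to 78.3%, but it implies a Day 15 SD of 0.5 × 15/104 = 0.07.

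Simulation with the unstructured covariance and complete data (3,000 trials per scenario) showed no bias of note. The model SE matched the empirical SE within about 3%. With a constant slope the by-visit term cost almost nothing (empirical SE 0.0853 against 0.0851).

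**Fallback.** A homogeneous structure fits approximately the mean of the visit variances, so SE ratio ≈ √(mean variance)/0.5.

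- Day 15 SD 0.25: SDs are 0.25, 0.309, 0.388, 0.5; mean variance 0.140; ratio 0.374/0.5 = 0.75; type I error 2[1 − Φ(1.96 × 0.747)] = 14%.
- Day 15 SD 0.35: SDs are 0.35, 0.385, 0.433, 0.5; mean variance 0.177; ratio 0.84; type I error 10%.
- Flat SD: ratio 1.00-1.03.
- SD proportional to √time: ratio 0.69-0.74; type I error 15-17%.

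Heterogeneous Toeplitz has its own variance at each visit; its ratio was 1.00-1.07 (1.01-1.02 with a subject effect).

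**The case against.** The strongest reply is that the common-slope model is valid, pre-specified in the protocol, and the simpler choice if the slope is stable. The sample size rests on an unadjusted t-test, so the planned 80% counts on no gain from baseline; in the table above, common-slope power never falls below the unadjusted 80.7%. All of this stands. It makes the point one of unused efficiency rather than error.

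A reader might infer that the model discards most of the baseline adjustment at Day 104. The documents do not support that. It needs a slope and an SD that both rise over visits, and they report neither.

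A reader might also infer that the fallback as a whole understates the Day 104 SE. That is wrong for heterogeneous Toeplitz, which comes first. AR(1) requires both the unstructured and the Toeplitz fits to fail. With 10 unstructured covariance parameters and about 128 patients, the unstructured model converged in every complete-data simulation. A smaller check with assumed dropout of 0%, 20% and 30% (100 trials each, not in SAS) saw no failure of either the unstructured model or Toeplitz with a subject effect. The SAP wording also leaves open whether the subject effect attaches to both fallbacks or to AR(1) alone.

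**Conclusion.** The point holds as a minor refinement. Leaving out baseline-by-visit may cost precision at Day 104: nothing with a constant slope, about 1 power point or less with a rising slope and flat SD, and roughly 1 to 8 points when both rise over the main assumed range. The estimate remains unbiased under randomisation; this was checked with complete data only. Every size depends on inputs that the documents do not give.

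The AR(1) weakness is real but conditional. It needs two prior non-convergences and an SD that grows with time. Given both, the Day 104 SE would be about 0.75-0.84 of its true value for a Day 15 SD of 0.25-0.35, with type I error about 10-14%. It is not a forecast of the error rate of the planned analysis.

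**What to change.** Add a baseline-by-visit interaction to the MMRM for CDR Sum of Boxes, MMSE and NPI. Make the change wherever the SAP states the model (9.5, 11.1, 11.2.4 and 11.2.5), and either align protocol 9.4.5 or record the departure in SAP section 8. The cost is 3 degrees of freedom, or 2 for NPI, which has no Day 15 assessment.

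Keep heterogeneous Toeplitz as first fallback, without the subject random effect. With it the structure has 8 parameters (4 variances, 3 correlations, 1 subject variance), and the subject variance is largely confounded with the Toeplitz correlations. Replace AR(1) with a heterogeneous-variance structure such as ARH(1) or heterogeneous compound symmetry, retaining Kenward-Roger. If empirical standard errors are preferred, name the degrees-of-freedom method that goes with them.

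No new data are needed. The edits should be made before unblinding, so that the choice cannot appear data-driven.
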